## **Secondary Outcome Measures:**

*Top choice diagnosis accuracy score* [Time Frame: Assessed at a single time point for each case, during the scheduled diagnostic reasoning evaluation session, which takes place between 0-4 days after participant enrollment.]

The secondary outcome will measure participants' performance in identifying the most likely diagnosis for each clinical vignette. After evaluating each case, participants will select their single most likely diagnosis, which will be scored on a pre-specified Three-Tier Diagnostic Accuracy Scale: 18 points for the most accurate diagnosis, 9 points for a clinically reasonable alternative, and 0 points for an incorrect diagnosis. For each participant, a Top Choice Diagnosis Accuracy Score is calculated as (total points earned  $\div$  maximum possible points) × 100, yielding a 0–100 % range in which higher scores indicate greater diagnostic accuracy. This percentage score will be compared at the case-level between randomized groups to quantify the impact of automation bias on diagnostic decision-making.

# Eligibility Criteria

Ages Eligible for Study: All

Sexes Eligible for Study: All

Accepts Healthy Volunteers: Yes

## Criteria

Inclusion Criteria:

- Completed Bachelor of Medicine, Bachelor of Surgery (MBBS) Exam. The equivalent degree of MBBS in US and Canada is called Doctor of Medicine (MD).
- Full or Provisionally Registered Medical Practitioners with the Pakistan Medical and Dental Council (PMDC).
- Participants must have completed a structured training program on the use of ChatGPT (or a comparable large language model), totaling at least 10 hours of instruction. The program must

include hands-on practice related to LLM's aspects, specifically prompt engineering and content evaluation.

## Exclusion Criteria:

• Any other Registered Medical Practitioners (Full or Provisional) with PMDC (e.g., Professionals with Bachelor of Dental Surgery or BDS).

## Potential Risks and Harms

This study poses minimal risk to participants. Some participants may experience mild discomfort or frustration, particularly those in the treatment group who may find clinical vignettes more challenging due to flawed LLM recommendations in a select set of vignettes.

#### Safeguards for Addressing Risks or Harms to Subjects

To minimize potential discomfort, participants will receive comprehensive instructions and ongoing support throughout the study. Participants will be explicitly informed that individual performance is not being evaluated, and that data will be analyzed for aggregate trends only. All participants will be advised of their right to withdraw from the study at any time without penalty or explanation. Research staff will monitor for signs of distress and provide appropriate support as needed.

#### **Informed Consent**

Informed consent will be obtained from all participants before enrollment in the study.

#### **Power Analysis:**

The minimum target sample size of 50 participants (25 participants per arm) was predetermined based on a prior study. The power analysis, conducted using Python version 3.11.9 (Python Software Foundation), employed the statsmodels.stats.power module from statsmodels version 0.14.4 (Statsmodels Developers) and indicated that a total sample of 200 to 250 completed cases (approximately 4 to 5 cases per participant) would provide at least 80% power to detect an 8-percentage-point mean difference in diagnostic reasoning scores, assuming a two-sided  $\alpha$  of .05. The analysis employed mixed-effects models suitable for cluster-randomized designs, considering an intraclass correlation coefficient (ICC) ranging from 0.05 to 0.15 and a standard deviation of 16.2%.

#### **Statistical Analysis:**

Descriptive analysis will be performed by comparing participant characteristics and automation bias behaviors between the treatment and control groups. Any categorical variables will be reported using counts and proportions, while continuous variables will be reported as means and standard deviations or, if their distribution is non-normal, as medians with interquartile ranges.

To understand automation bias behavior the following descriptive statistics will be reported for both the study groups:

• *Proportion of clinical vignettes in which participants accessed LLM suggestions: For each of the six vignettes, a binary indicator will be recorded (1 = participant clicked to view the LLM's suggestions; 0 = no access). The final measure is the mean proportion of vignettes (range 0–1) per participant for which suggestions were accessed.* 

- *Proportion of clinical vignettes in which participants copy-pasted LLM suggestions: For each of the six vignettes, a binary indicator is recorded:* 
  - 1 = participant directly copy-pasted the LLM's suggestion into their diagnostic answer (i.e., accepted verbatim without any edits)
  - $\circ$  0 = no direct copy-paste occurred

The final measure is calculated as the mean proportion of vignettes (range 0-1) per participant in which suggestions were copy-pasted.

• *Mean fraction of questions per vignette answered via direct copy-paste of LLM suggestions*: For each vignette, we will calculate the fraction of questions that were copy-pasted by dividing the number of copy-pasted answers by the total of five questions per vignette. The final measure is the average of these vignette-level fractions across all six vignettes, yielding a single measure per participant that ranges from zero (no copy-pasting) to one (all questions copy-pasted).

The primary outcome analysis will be conducted at the case level, with clustering by participant under an intention-to-treat framework. The primary analysis will be based on cases with completed responses only. We will first summarize the mean and standard deviation of scores (standardized on a 0–100 scale) and report the mean and standard deviation for the time spent on each case, both for the overall cohort and separately for each of the study arms. To evaluate the impact of the treatment (i.e., providing access to recommendations some which contain inaccurate information), we will apply generalized mixed-effect models, including a random effect for the participant to account for potential within-participant correlation between cases, and a random effect for cases to account for differences in difficulty across cases. To improve precision, we will include the following covariates as control variables: past experience in LLM use, gender, and years of practice post MBBS. We will also conduct the following sensitivity analyses to assess the robustness of the findings:

- 1) Effect sizes without controls
- 2) The primary outcome analysis will be repeated including incomplete cases (if any) to evaluate the potential impact of missing data (e.g., using multiple imputation).
- 3) Inter-rater reliability for the diagnostic reasoning scores across at least two raters will be assessed using Cohen's kappa or Fleiss' kappa depending on the final number of raters.
- 4) The internal consistency of the diagnostic reasoning score across the six vignettes will be assessed using Cronbach's alpha.
- 5) Assessment of normality assumptions

For the secondary outcome (top choice diagnosis accuracy score), a mixed-effects ordinal logistic regression model will be used, with the same random effects structure as the primary analysis, and the dependent variable being the three-level final diagnosis accuracy (Incorrect, Partially Correct, Correct).

A secondary analysis will be conducted to measure the sequential trend in automation bias. A linear mixedeffects model will be used, with random intercepts for participants and for vignettes, and fixed effects for vignette order, treatment arm, and their interaction. The dependent variable will be the vignette-level diagnostic reasoning performance (percentage); the sequence-by-treatment interaction will then quantify how the treatment arm's trajectory deviates from control, reflecting any progressive automation bias across successive vignettes. We will repeat this analysis for the secondary outcome as well.

Subgroup analyses will be performed based on experience with LLMs, gender and years of practice post MBBS. Scores for each case question will also be compared descriptively between the two randomized groups.

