#### Arms and Interventions

Arm	Intervention/Treatment
Active Comparator: ChatGPT-40	Other: ChatGPT-40 Recommendations with
Recommendations with Hallucinations	Hallucinations
Participants will evaluate six clinical vignettes.	
During the trial, they will have access to clinical	ChatGPT-40's differential diagnoses of six clinical
recommendations from a specific, commercially	vignettes, three of which will contain deliberately
available LLM (ChatGPT-40) in addition to	introduced inaccurate information.
conventional diagnostic resources. LLM	*
recommendations for three vignettes will contain	
deliberately flawed diagnostic information and for	
three vignettes it will contain accurate	
recommendations). The cases will be presented in	
random order.	
No Intervention: ChatGPT-40 Recommendations	
without Hallucinations	
Participants will evaluate the same six clinical	
vignettes as in the intervention arm. During the	
trial, they will have access to clinical	
recommendations from a specific, commercially	
available LLM (ChatGPT-40) in addition to	
conventional diagnostic resources. However, the	
LLM-generated recommendations will not contain	
any deliberately introduced errors. The cases will	
be presented in random order.	

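### Both copy-paste measures pool vignettes with and without planted errors, so as descriptions of automation bias they cannot separate accepting flawed advice from accepting sound advice

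*Combined protocol and SAP*

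**What the plan says.** The Statistical Analysis section introduces its behaviour measures with the words "To understand automation bias behavior the following descriptive statistics will be reported for both the study groups". Three follow: access to the LLM's suggestions, any copy-paste in a vignette, and the fraction of a vignette's questions answered by copy-paste.

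This point concerns the last two. For any copy-paste, code 1 means "participant directly copy-pasted the LLM's suggestion into their diagnostic answer (i.e., accepted verbatim without any edits" and code 0 means "no direct copy-paste occurred"; the indicators are averaged to one proportion per participant. The fraction measure is obtained by "dividing the number of copy-pasted answers by the total of five questions per vignette", and the participant's value is the "average of these vignette-level fractions across all six vignettes". Neither definition refers to whether the copied advice was sound.

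Arms and Interventions says that the treatment arm receives differential diagnoses for six clinical "vignettes, three of which will contain deliberately" introduced inaccuracies. The control arm sees the same six vignettes with no planted errors. Exploratory Analyses plans a within-participant contrast of flawed and unflawed vignettes, with the corresponding contrast in control, but only for the diagnostic reasoning score.

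**The concern.** The trial plants errors so that warranted reliance on the LLM can be told apart from acceptance of wrong advice. The copy-paste records are its direct observation of that acceptance, but the planned summaries give a copied correct answer and a copied planted error the same weight. Half of the treatment-arm vignettes and all of the control-arm vignettes carry advice without deliberate errors, so most of what these measures count is not acceptance of a planted error.

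The direction of the distortion matters. Doctors who notice planted errors should copy less on those vignettes, so similar copying in the two arms on the flawed set would itself suggest bias. Pooling adds three vignettes on which the arms received equally sound advice. This pulls the arms together and can imitate that sign.

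**Working it through.** **The plan's own figure.** The plan gives none for the behaviour measures. Its stated figure, at least 80% power for 8 points, belongs to the primary score. It is reproduced here only to show that this point leaves it alone. Inputs from Power Analysis: SD 16.2, two-sided α 0.05, ICC 0.05 to 0.15, 200 to 250 completed cases, 50 participants.

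With m = cases/50, effective n per arm = (cases/2) / (1 + (m − 1) × ICC), and power = Φ(8 / (16.2 × √(2/n)) − 1.96).

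- 200 cases, m = 4: 100/1.15 = 87.0 gives 90.3%; 100/1.45 = 69.0 gives 82.6%.
- 250 cases, m = 5: 125/1.20 = 104.2 gives 94.6%; 125/1.60 = 78.1 gives 87.0%.

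The stated figure holds, and no copy-paste measure enters it.

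**One treatment-arm participant.** There are three flawed and three accurate vignettes.

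- Copies in every flawed vignette and no accurate one: (3×1 + 3×0)/6 = 0.50.
- Copies in every accurate vignette and no flawed one: (3×0 + 3×1)/6 = 0.50.

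The fraction measure gives the same result if all five answers are copied where copying occurs, since each such vignette contributes 5/5 = 1.

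**Arm level.** Let c and f be the treatment arm's copy rates on the accurate and flawed sets, and k_A and k_F the control arm's rates on the same two sets of vignettes.

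- Pooled arm difference = (3c + 3f)/6 − (3k_A + 3k_F)/6 = ½(c − k_A) + ½(f − k_F).
- If c = k_A, this is ½(f − k_F): exactly half of the flawed-set difference, whatever the rates.
- Difference of differences = (f − c) − (k_F − k_A).

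The documents give no copy rates, so those below are assumptions chosen for illustration, with k_A = k_F = k.

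| c | f | k | Pooled, treatment | Pooled difference | Flawed-set difference | Difference of differences |
|---|---|---|---|---|---|---|
| 0.5 | 0.5 | 0.5 | 0.50 | 0 | 0 | 0 |
| 0.5 | 0.2 | 0.5 | 0.35 | −0.15 | −0.30 | −0.30 |
| 0.35 | 0.35 | 0.5 | 0.35 | −0.15 | −0.15 | 0 |
| 0.8 | 0.2 | 0.8 | 0.50 | −0.30 | −0.60 | −0.60 |
| 0.2 | 0.8 | 0.2 | 0.50 | +0.30 | +0.60 | +0.60 |

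The first, fourth and fifth rows share a pooled treatment value of 0.50, with flawed-set rates of 0.5, 0.2 and 0.8. The second and third rows agree even on the pooled arm difference. The second describes doctors who reject flawed advice selectively; the third describes doctors who copy less everywhere. Only the split tells them apart.

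**The case against.** The strongest reply is that these are descriptive summaries and not the trial's measure of automation bias. The Detailed Description quantifies bias by the difference in diagnostic accuracy scores between arms, and the flawed/unflawed contrast is already planned for the score. That document also describes automation bias broadly, as over-reliance on technology, without requiring the advice to be wrong. On that view unedited copying is informative whatever its content, and the control values are meaningful. This stands as a defence of the pooled figures as measures of general reliance, and it limits how serious the point is. It does not supply what is missing: no planned summary shows whether planted errors were copied.

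Three stronger readings are tempting, and the documents do not support them.

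- *That the access measure has the same fault.* Access is a click to view the suggestions, made before the doctor can see whether that vignette's advice is flawed. It cannot be acceptance of a planted error.
- *That vignettes never reached are counted as no use.* A reader might infer this from the 0/1 coding and the fixed denominator. If a participant copied in every vignette reached, and reached 4 or 5, coding the rest 0 would give 4/6 = 0.67 or 5/6 = 0.83 instead of 1.00. But nothing in the plan says that unreached vignettes are coded 0, and the general missing-data text under Exploratory Analyses allows them to be treated as missing. The "approximately 4 to 5 cases per participant" in Power Analysis is a number of completed cases sufficient for power. It does not forecast how many vignettes are opened.
- *That such a shortfall would differ by arm.* The documents give no basis for this.

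**Conclusion.** The point holds for the two copy-paste measures. As defined, they give 0.50 to opposite behaviours, and they halve any arm difference confined to flawed vignettes. The first result follows from the definitions alone. The halving needs the treatment arm to behave like control on the accurate set, and the move from 30 points to 15 also uses assumed copy rates of 0.5 and 0.2. Whether that equality holds cannot be seen from the pooled figures.

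The consequence is confined to interpreting descriptive behaviour results. The primary test, its power and the secondary outcome are unaffected, and the pooled measures remain valid as summaries of general reliance. How unreached vignettes are handled is not stated; that is a matter for clarification and not a demonstrated error.

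**What to change.** Keep the pooled copy-paste figures, described as general reliance. In addition:

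- Report both copy-paste measures separately for the flawed-set and accurate-set vignettes in each arm. In control, the flawed set means the same three vignettes, shown there without planted errors.
- Compare the arms on the flawed set.
- As evidence of selective rejection, take the treatment arm's flawed-minus-accurate difference minus the same difference in control. The within-arm difference alone will not do, because the two sets may differ in difficulty.
- Label these results descriptive. As Study Design gives actual completion dates in July 2025, label them post hoc as well.
- As a secondary clarification, state how unreached vignettes are handled and report by arm how many vignettes contribute to each measure.

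The access measure need not be split. The copy-paste data are already defined vignette by vignette, so the split needs no new data collection. The cost is a few more table rows.

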This randomized controlled trial (RCT) aims to systematically measure the extent and patterns of automation bias among physicians when utilizing ChatGPT-40 in clinical decision-making. The investigators will assess how access to LLM-generated information influences diagnostic reasoning through a novel methodology that precisely quantifies automation bias. In this study, participants will be randomly assigned to one of two groups. The treatment group will receive LLM-generated recommendations containing deliberately introduced errors in a subset of cases, while the control group will receive LLM-generated recommendations without such deliberately introduced errors. Participants will evaluate six clinical vignettes randomly sequenced to prevent detection patterns. The flawed vignettes provided to the treatment group will incorporate subtle yet clinically significant errors that should be identifiable by trained doctors. This will enable investigators to quantify the degree of automation bias by measuring the differential in diagnostic accuracy scores between the treatment and control groups.

Prior to participation, all physicians will complete a comprehensive training program covering LLM capabilities, prompt engineering techniques, and output evaluation strategies. Responses will be evaluated by blinded reviewers using a validated assessment rubric specifically designed to detect uncritical acceptance of erroneous information, with greater score disparities indicating stronger automation bias. This naturalistic approach will yield insights directly applicable to real clinical workflows, where mounting cognitive demands may progressively impact diagnostic decision quality.

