## Study Design

Study Type: Interventional (Clinical Trial)

Actual Enrollment: 50 participants

Allocation: Randomized. Randomization list was created by [name] using the Sealed Envelope program.

Intervention Model: Parallel Assignment

Intervention Model Description: The trial will be designed as a randomized, two-arm, single-blind parallel group study.

Masking: Single (Outcomes Assessor)

Masking Description: The grading of responses will be performed by assessors blinded to participant identity and treatment assignment.

Primary Purpose: Diagnostic

Official Title: Trust or Verify? Automation Bias in Physician-LLM Diagnostic Reasoning

Actual Study Start Date: June 5, 2025

Actual Primary Completion Date: July 1, 2025

Actual Study Completion Date: July 15, 2025

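### The primary arm effect averages over three flawed and three accurate vignettes, yet the plan reads arm differences as automation bias and models no arm contrast on the flawed three

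*Combined protocol and SAP*

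**What the plan says.** **Design.** Under Arms and Interventions, both arms evaluate the same six vignettes. The treatment arm receives ChatGPT output on all six, "three of which will contain deliberately" introduced inaccuracies. The control arm's output has no planted errors.

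**Primary model.** Under Statistical Analysis: "To evaluate the impact of the treatment (i.e., providing access to recommendations some which contain inaccurate information), we will apply generalized mixed-effect models". The model has random effects for participant and case, and three participant covariates (LLM experience, gender, years of practice). It has no term for vignette type. "The primary analysis will be based on cases with completed responses only".

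**Interpretation.** The Detailed Description says: "The flawed vignettes provided to the treatment group will incorporate subtle yet clinically significant errors that should be identifiable by trained doctors". The next sentence says that this will let the investigators "quantify the degree of automation bias by measuring the differential in diagnostic accuracy scores between the treatment and control groups". Of the top-diagnosis score, Secondary Outcome Measures says: "This percentage score will be compared at the case-level between randomized groups to quantify the impact of automation bias on diagnostic decision-making".

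**Other analyses.** The ordinal model for the secondary outcome has no vignette-type term. The sequential-trend model interacts arm with vignette order, not type. Scores for each case question are compared descriptively. Exploratory Analyses lists the within-subject difference between flawed and unflawed vignettes, set against the corresponding control-arm difference. It covers the diagnostic reasoning score only and names no model.

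**Power.** The Power Analysis states that 200 to 250 completed cases "would provide at least 80% power to detect an 8-percentage-point mean difference in diagnostic reasoning scores", with SD 16.2 and ICC 0.05 to 0.15.

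**The concern.** Automation bias, as the plan describes it, is over-reliance on the tool, and the planted errors are what expose it. They sit in half of the treatment arm's vignettes. A single arm coefficient over all six mixes the loss where advice was wrong with any change where advice was right. Such a change (spillover) could go either way: lost trust after spotting an error, for example, or extra vigilance.

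The coefficient answers the question that the Statistical Analysis section poses. It does not by itself answer the one posed in the Detailed Description. If that section means the flawed-vignette difference, as its preceding sentence allows, then no planned model estimates it.

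Two wrong readings become possible. A diluted net effect may be reported as the degree of automation bias, or a null net effect may be reported as its absence.

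**Working it through.** **Inputs from the documents.** 25 participants per arm, SD 16.2, ICC 0.05 to 0.15, two-sided α 0.05 (Power Analysis); three of six vignettes flawed (Arms and Interventions).

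**Assumptions.** Same SD and ICC in both vignette types, no covariate gain, equal completion unless stated. The documents give no spillover value; zero is the base case. Effects are written as losses.

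**1. The plan's own figure.** With m completed cases per participant, the standard error of the arm difference is

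SE = √(2 × 16.2² × (1 + (m − 1) × ICC) / (25m)),

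and power comes from the noncentral t distribution with 48 df. For an 8-point all-case difference:

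| Cases | ICC 0.05 | ICC 0.10 | ICC 0.15 |
|---|---|---|---|
| 200 (m = 4) | 89% | 85% | 81% |
| 250 (m = 5) | 94% | 90% | 86% |
| 300 (m = 6) | 96% | 93% | 89% |

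The claim of at least 80% is reproduced.

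**2. What the coefficient mixes.** Let D be the loss on the flawed three and s the loss on the accurate three. With three completed cases of each type, the primary coefficient is (D + s)/2. The exploratory within-subject comparison estimates D − s.

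| D | s | Primary (D + s)/2 | Exploratory D − s |
|---|---|---|---|
| 16 | 0 | 8 | 16 |
| 12 | 4 | 8 | 8 |
| 8 | 8 | 8 | 0 |

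The same primary result fits all three rows. The exploratory contrast equals D only in the first.

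**3. Precision of the three contrasts, six cases each.**

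- All six (m = 6): SE 2.09 / 2.29 / 2.47 at ICC 0.05 / 0.10 / 0.15. At ICC 0.10, √(2 × 262.44 × 1.5 / 150) = 2.29.
- Flawed three (m = 3): SE 2.77 / 2.90 / 3.02. At ICC 0.10, √(2 × 262.44 × 1.2 / 75) = 2.90.
- Exploratory contrast: SE = √(4 × 16.2² × (1 − ICC) / 75) = 3.65 / 3.55 / 3.45.

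**4. Power with no spillover (s = 0).** Ranges run over ICC 0.05 to 0.15.

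| D | All six (effect D/2) | Flawed three | Exploratory contrast |
|---|---|---|---|
| 8 | 35–47% | 74–81% | 57–62% |
| 12 | 66–80% | 97–99% | 90–93% |
| 16 | 89–96% | above 99% | 99% or more |

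The 8-point row is an illustration, not the plan's target. The 16-point row corresponds to the plan's 8-point all-case average. With the SD 20% higher, the 8-point figures for all six and the flawed three fall to 26–35% and 58–65%. A simulation of 20,000 trials per ICC agrees with the all-six and flawed-three figures in the 8-point row within one percentage point.

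**5. Unequal completion.** The primary analysis uses completed cases only. If 250 cases split 3:2 flawed to accurate in both arms, an 8-point flawed effect gives a coefficient of 8 × 3/5 = 4.8; at 2:3 it gives 8 × 2/5 = 3.2. An 8-point all-case difference then corresponds to 8/0.6 = 13.3 or 8/0.4 = 20.0 points on the flawed vignettes, instead of 16.

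**The case against.** The strongest reply is that nothing in the primary analysis is wrong. The arm effect is randomised, the Statistical Analysis section describes it accurately, and the power figure holds. All of that stands, and the primary should not change.

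The interpretive wording can also be read more kindly. The sentence in the Detailed Description follows directly on one about flawed vignettes, and the secondary-outcome sentence could mean a net consequence over the case set. Both readings are possible. On the first, the plan still lacks a model for the contrast it means.

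Vignette type is not ignored either. The exploratory comparison separates it for the primary score, removes chance differences in participant ability between arms, and has 90–93% power at 12 points and about 99% at 16 if there is no spillover. Flawed-three means by arm could be derived from it. This narrows the gap without closing it: the analysis is exploratory, omits the secondary outcome, and subtracts any spillover instead of showing it. For the secondary outcome there is only the descriptive comparison of question scores. The absence of a planned interval is not peculiar to this analysis, since the plan names confidence intervals for none.

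Finally, the low power figures rest on an 8-point flawed-only benchmark that the plan does not use. That is fair: they illustrate dilution and do not show that the trial is underpowered.

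**Conclusion.** The concern holds, as a mismatch between what is estimated and how it is to be read. The primary coefficient is a valid net effect of partly flawed advice; it is not by itself the degree of automation bias. With no spillover and equal completion it is half the loss on the flawed vignettes, and with unequal completion or spillover the ratio changes. At the plan's target of 8 points over all cases, power is adequate and only interpretation is at issue. If the loss were 8 points on the flawed vignettes alone, the primary test would have 35–47% power, so a null result could accompany a material loss where the advice was wrong. These figures rest on the plan's SD and ICC applying to both vignette types. The point should be fixed, but it does not invalidate the primary analysis.

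**What to change.** - Keep the all-six arm effect as primary. In a dated amendment, describe the arm comparisons in the Detailed Description and Secondary Outcome Measures as the net effect of partly flawed advice.
- Add to the primary mixed model a flawed-vignette indicator, with the same vignettes labelled in both arms, and its interaction with arm. Report with confidence intervals the arm contrast on the flawed three (the automation-bias estimate) and on the accurate three (the spillover check).
- Do the same in the ordinal model for the secondary outcome.
- Label all these contrasts as supplementary, with no rank above the other non-primary analyses. Study Design gives "Actual Study Completion Date: July 15, 2025", so they cannot be called pre-specified.
- Optionally, state in the Power Analysis that 8 points is an all-case average, equal to 16 on the flawed vignettes if there is no spillover and completion is equal.

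**Cost.** No new data: some rewording, one indicator with its interaction in two models, and four extra contrasts. The flawed-three contrast uses half the cases (SE 2.8–3.0 against 2.1–2.5) and does not reach 80% power for 8 points across the whole ICC range. The spillover check is imprecise: its 95% interval is about ±5.6 to ±6.1 points (2.011 × 2.77 to 3.02). These standard errors apply to these particular vignettes; generalising to others would need wider intervals if the arm effect varies between vignettes. No precision was computed for the ordinal contrasts.

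### The primary model has no term for vignette position, so the arm effect can be biased if the arms complete different numbers of cases and scores change along the sequence

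*Combined protocol and SAP*

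**What the plan says.** Under Statistical Analysis, the primary model contains arm, a random effect for participant and "a random effect for cases to account for differences in difficulty across cases". For precision, "we will include the following covariates as control variables: past experience in LLM use, gender, and years of practice post MBBS". No term represents when in the sequence a case was seen. The same section says: "The primary analysis will be based on cases with completed responses only".

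The Detailed Description says: "Participants will evaluate six clinical vignettes randomly sequenced to prevent detection patterns". The Power Analysis rests on "200 to 250 completed cases (approximately 4 to 5 cases per participant", so its requirement can be met with one or two of the six cases missing per participant.

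Position is not foreign to the plan. The Detailed Description raises the possibility that mounting cognitive load affects decisions progressively. A secondary analysis under Statistical Analysis fits "fixed effects for vignette order, treatment arm, and their interaction", so position has to be recorded.

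On missing data, Statistical Analysis repeats the primary analysis with incomplete cases included, for example by multiple imputation. Exploratory Analyses describes missing-data patterns and calls for imputation when more than 5% of a key variable is missing. Neither section says whether position enters the imputation model.

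**The concern.** Random ordering makes position independent of which vignette is seen, and balances position between arms as long as both arms complete the same cases. Completion is observed after randomization, and arm may affect it. If participants stop before the end, the lost cases are the late ones. An arm that stops sooner is then scored at earlier positions on average.

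The case random effect does not repair this, because it adjusts for which vignette was answered and not for when. A mixed model tolerates missing outcomes when missingness depends only on quantities in the model, and position is not one of them.

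The estimate at stake is the primary one. If scores fall along the sequence and the treatment arm stops earlier, part of the automation bias is hidden. If the control arm stops earlier, it is exaggerated.

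**Working it through.** **Inputs from the plan.** "The minimum target sample size of 50 participants (25 participants per arm"; six cases each in random order; 8-point difference; SD 16.2; ICC 0.05 to 0.15; two-sided alpha 0.05.

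**Assumed, because the plan gives no figure.** The change in score per position; mean completed cases by arm; unfinished cases being the last ones.

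**Step 1: the plan's own power figure.** With m cases per participant, the effective number per arm is 25m / [1 + (m − 1) × ICC].

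- At m = 4 and ICC 0.15: 100 / 1.45 = 69.0; SE = 16.2 × √(2/69.0) = 2.76; 8/2.76 = 2.90; power = Φ(2.90 − 1.96) = 82.6%.
- 200 cases: 90.3%, 86.5% and 82.6% at ICC 0.05, 0.10 and 0.15.
- 250 cases: 94.6%, 91.0% and 87.0%.
- With a t distribution on 48 df, the lowest value is 81.1%.

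The stated figure of at least 80% reproduces.

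**Step 2: size of the shift under a common trend.** A participant who completes the first k cases has mean position (k + 1)/2. With slope b per position in both arms, the shift in treatment minus control is b × (k_T − k_C)/2.

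- b = −1: 4 v 5 gives −1 × (−0.5) = +0.5; 4 v 6 gives +1.0.
- b = −2: 4 v 5 gives +1.0; 4 v 6 gives +2.0.
- b = −2 with control stopping earlier (5 v 4): −2 × 0.5 = −1.0.

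The expected effect is negative, so a positive shift is toward zero.

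**Step 3: simulation.** 600 trials per setting, 25 per arm, true effect −8, ICC 0.10, case variance 10% of the total (assumed), crossed participant and case effects, generalized least squares with known variances, and position as a linear term. Monte Carlo error is about 0.1.

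| Slope per position | Cases, T v C | Formula | Bias without position | Bias with position | SE without → with |
|---|---|---|---|---|---|
| −1 both arms | 4 v 5 | +0.5 | +0.36 | −0.16 | 2.43 → 2.46 |
| −2 both arms | 4 v 5 | +1.0 | +0.86 | −0.12 | 2.43 → 2.46 |
| −2 both arms | 5 v 6 | +1.0 | +0.85 | −0.15 | 2.28 → 2.29 |
| −1 both arms | 4 v 6 | +1.0 | +0.96 | −0.09 | 2.37 → 2.45 |
| −2 both arms | 4 v 6 | +2.0 | +2.05 | +0.05 | 2.37 → 2.45 |
| −2 both arms | 4.5 v 4.5 | 0 | +0.09 | +0.10 | 2.42 → 2.42 |
| −2 both arms | 6 v 6 | 0 | +0.05 | +0.05 | 2.21 → 2.21 |
| none | 4 v 6 | 0 | −0.03 | −0.01 | 2.37 → 2.45 |

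**Step 4: trend in one arm only.** With slopes of −2 in treatment and 0 in control, the target is the effect averaged over all six positions.

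- 4 v 6: bias is +2.07 without position and +1.59 with a linear main effect. A second run gave +2.08 and +1.97. Only position-by-arm, read at mid-sequence, removes it (+0.08, SE 2.71).
- Equal completion at 4.5 cases: still a shift of +1.37, because both arms then lack late positions and only one has a trend.

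**Step 5: consequence for power.** At 4.5 cases per participant:

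| Apparent difference | Power, ICC 0.05 | Power, ICC 0.15 |
|---|---|---|
| 8 points | 92.7% | 85.1% |
| 7 points | 84.8% | 74.7% |
| 6 points | 72.7% | 61.4% |

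**The case against.** The strongest reply is that the conditions for bias are nowhere shown to hold. The 4 to 5 cases per participant is a number sufficient for power and not a forecast that people will stop early. Everyone is given six vignettes, and the plan refers to incomplete cases only as a possibility. No session time limit is stated, so nothing in the text makes the treatment arm finish fewer cases. An incomplete case might also be partly answered rather than last in line. A decline along the sequence is posed as a question, without a size. All of this stands. A reader might infer that the primary arm effect is biased, or that the plan counts on early stopping; the documents support neither.

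The second reply is that safeguards exist. The order-by-arm model would show a trend, the missing-data description would show uneven completion, and time per case is reported by arm. If 4 or 5 of six cases were completed, 33% or 17% would be missing, well above the 5% trigger for imputation. This stands in part, because these steps could expose the problem but do not correct the primary estimate. The order-by-arm model is secondary, targets the interaction, and states no position at which its arm effect is read. The imputation is a comparison analysis and does not name position.

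The third reply is that a position main effect does little when only the treatment arm declines, which the plan's trend analysis allows for. Step 4 confirms this, so the fix needs a second part.

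**Conclusion.** The point holds as a conditional one and is a low-cost improvement, not a fatal flaw. The primary estimate is unprotected against unequal completion combined with a trend along the sequence.

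Under a common decline of 1 to 2 points per position, the shift is 0.5 to 1.0 point for one case of difference in mean completion and 1 to 2 points for two. That compares with a target of 8 and a standard error of about 2.4; a steeper decline scales it in proportion. Its direction depends on which arm stops earlier. It is nil with no trend, or with a common trend and equal completion.

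These sizes rest on three assumptions that the documents do not settle: the slope, the completion gap, and unfinished cases being the late ones. The corresponding shift in the secondary ordinal model was not quantified.

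**What to change.** - Add vignette position (1 to 6) as a fixed effect in the primary mixed model and in the secondary ordinal model, stating in advance whether it is linear or categorical.
- Report the version without position as its own labelled sensitivity analysis, separate from the planned analysis that drops the three covariates.
- Include position in any imputation model.
- Report completed cases by arm and by position.
- Add a sensitivity analysis with position-by-arm, giving the arm effect averaged over all six positions. For an arm that rarely reached the last positions, this average relies on the assumed form of the trend.

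**Cost.** One term on a variable that the trend analysis already needs. In the unequal-completion settings in the table, a linear term raises the standard error by up to about 3% (2.45/2.37 = 1.03). Allowing for how position is coded, about 2 to 6% is a fair planning range. The cost is nil when all six cases are completed. The position-by-arm analysis is dearer (2.71/2.37 = 1.14 at 4 v 6), which is why it belongs among the sensitivity analyses. Since Study Design gives actual completion dates, the record should show when the change was made and whether results by arm had been seen by then.
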